4.5. Handling Data From Patients who Withdraw and Re-Enter the Study

Patients who terminate early from the study due to emergency circumstances (such as coronavirus disease 2019 [COVID-19]) may be allowed to re-enter the study at a later date.

Patients re-entering the study will redo the entire study from the start.

4.5.1. Baseline Values

In general, baseline values from the re-entered participation will be used. Missing baseline values will be handled in the same method as other non-withdrawal patients.

Results from the original participation of the CYP2D6 impairment status at baseline will be carried over to the repeated participation (re-entered) portion.

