The TEV-50717 tablets cannot be crushed or split but should be swallowed whole; the TEV-50717 tablets should be taken with food (eg, a snack) and should not be taken on an empty stomach. The titration scheme and maximum dose will be determined by body weight at day 1 and CYP2D6 impairment status, as shown in [Table 6](#) and [Table 7](#), respectively. Patients will be classified as CYP2D6 impaired if they are receiving a strong CYP2D6 inhibitor. Patients who are CYP2D6 impaired will have a dose cap in the open-label study, as shown in [Table 7](#).

Patients and their caregiver will interact weekly with the clinical research staff, either by telephone contact (with non-recording live video) or in-clinic visits from week 1 through week 7 of the titration period, in order to evaluate safety and establish a dose of TEV-50717 that optimally reduces dyskinesia (as indicated by a reduction in the CGI-I) and is well tolerated (optimal dose). The telephone contacts to the patient will be supported by live video stream, without recording, to provide visual confirmation to the investigator of the verbal information provided by the patient or caregiver. Safety evaluations during the titration period include assessment of vital signs, monitoring for adverse events and concomitant medications, 12-lead ECGs, identifying patients at risk for suicide, assessment of drug-induced parkinsonism according to the ESRS (subsubscales I and II), assessment of change in behavior according to the CBCL questionnaire, and assessment of sedation according to the ESS questionnaire.

In-person (in-clinic) study visits will be scheduled at weeks 3 and 7, and telephone contacts (with non-recording live video) will be scheduled for weeks 1, 2, 4, 5, and 6 in order to assess dyskinesia and adverse events.

The dose of TEV-50717 should be increased to reach a clinically meaningful reduction in dyskinesia, as indicated by a reduction in the CGI-I (see [Table 6](#)). The dose of TEV-50717 should not be increased further if either of the following occurs:

- the patient experiences a “clinically significant” adverse event (defined as an adverse event that is related to TEV-50717 and is either moderate or severe in intensity or meets the criteria for a serious adverse event), OR
- the maximum allowable dose is reached based on the patient’s weight and CYP2D6 impairment status at day 1. Patients will be classified as CYP2D6 impaired if they are receiving a strong CYP2D6 inhibitor.

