**Table 7: Maximum Daily Dose of TEV-50717 by CYP2D6 Impairment Status**

Weight category	Maximum daily dose in the absence of CYP2D6 impairment	Maximum daily dose in the presence of CYP2D6 impairment
12 kg to <17 kg (26 lbs to <37 lbs)	24 mg	12 mg
17 kg to <30 kg (37 lbs to <66 lbs)	30 mg	18 mg
30 kg to <40 kg (66 lbs to <88 lbs)	42 mg	24 mg
≥40 kg (≥88 lbs)	48 mg	36 mg

CYP2D6=cytochrome P450 2D6.

Note: Patients will be classified as CYP2D6 impaired if they are receiving a strong CYP2D6 inhibitor. Strong CYP2D6 inhibitors include paroxetine, fluoxetine, and bupropion.

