### **Section 4.3 Withdrawal Criteria and Procedures for the Patient**

In the event of an emergency situation (eg, the COVID-19 pandemic), in case a patient cannot return to the clinic for the scheduled visits (eg, due to quarantine, isolation, patient's concern, or closure of the site clinic), patients who cannot complete their ECG assessments during the titration period (local or at site) at week 3 and week 7 visits will be early terminated from the study. In addition, patients who cannot complete the Columbia-Suicide Severity Rating Scale (C-SSRS) and pregnancy test as per protocol will also be early terminated from the study.

In the event the patient cannot continue in the study due to the current emergency situation (eg, the COVID-19 pandemic), the patient will be terminated early from the study. However, patients may be allowed to re-enter the study as soon as the current emergency situation (eg, the COVID-19 pandemic) permits, following approval by the medical monitor and full screening assessments. As a consequence, it is possible that a patient may participate in the study for longer than initially planned and, therefore, may receive treatment for more than 53 weeks.

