The titration scheme and maximum dose will be determined by body weight at day 1 and cytochrome P450 2D6 (CYP2D6) impairment status. Patients will be classified as CYP2D6 impaired if they are receiving a strong CYP2D6 inhibitor. Patients who are CYP2D6 impaired will have a dose cap in the open-label study. Safety evaluations during the titration period include assessment of vital signs, monitoring for adverse events and concomitant medications, 12-lead electrocardiograms (ECG)s, identifying patients at risk for suicide, assessment of drug-induced parkinsonism according to the Extrapyramidal Symptom Rating Scale (ESRS) subscales I and II, assessment of change in behavior according to the Child Behavior Checklist (CBCL) questionnaire, and assessment of sedation according to the Epworth Sleepiness Scale (ESS) questionnaire.

In-person (in-clinic) study visits will be scheduled at weeks 3 and 7, and telephone contacts (with non-recording live video) will be scheduled for weeks 1, 2, 4, 5, and 6 in order to assess dyskinesia and adverse events.

Maintenance period (46 weeks): At the end of the titration period (week 7), the patient's initial dose for the maintenance period (up to week 53) will be established. Dose adjustments of TEV-50717 (upward or downward) may be made during the maintenance period, if necessary, based on efficacy, safety, and/or tolerability considerations but not more often than every 5 days and only in increments of 6 mg up to the maximum allowed dose (see [Table 6](#) and [Table 7](#)).

[figure not shown]
During the maintenance period, in-person (in-clinic) study visits will be scheduled at weeks 14, 27, 40, and 53 for assessments of safety and efficacy, and telephone contacts (with non-recording live video) will be scheduled for weeks 21, 33, and 46 in order to assess adverse events and dyskinesia. At week 53/early termination (ET), patients will undergo a complete evaluation.

Washout and follow-up period: All patients should continue their usual treatment regimen up to week 53 visit (ie, the last dose can be administered until visit completion, if applicable). No dosing will be given after the week 53 visit. All patients will discontinue TEV-50717 at the week 53 visit and will return 1 week later (week 54) for evaluation of safety. Patients will have a follow-up telephone contact (no live video streaming) for safety evaluation 1 week after the end of the washout period (2 weeks after their last dose of TEV-50717) (week 55).

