5.7. Study Drug Titration

The number and percent of patients at each dose level by weight group and CYP2D6 impairment status during the titration period will be summarized by week. The latest administered dose in each study week will be used.

Reasons for the deviation from the IMP administration will be summarized overall and by period (titration and maintenance).

Descriptive statistics of the maintenance dose (last dose taken in the maintenance period; nominal and as percent of the maximal planned dose for the patient) will be presented.

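### SAP 4.5.1 gives re-entering patients their old CYP2D6 impairment status, although the study defines status by inhibitor use and fixes it at day 1

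*SAP*

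**What the plan says.** SAP 4.5 covers patients who terminated early because of an emergency and later return: "Patients re-entering the study will redo the entire study from the start". SAP 4.5.1 gives the general rule, "In general, baseline values from the re-entered participation will be used", and then the exception: "Results from the original participation of the CYP2D6 impairment status at baseline will be carried over to the repeated participation (re-entered) portion". No other variable is named as an exception. Under SAP 4.5.2, only data from the repeated participation enter the ITT set; data from the original participation are listed and kept out of the summary tables.

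The definition of impairment is the same in both documents. SAP 2.1 says "Patients will be classified as CYP2D6 impaired if they are receiving a strong CYP2D6 inhibitor", and the note to Protocol Table 7 repeats it. Protocol Section 3.1 (titration period) ends escalation when "the maximum allowable dose is reached based on the patient’s weight and CYP2D6 impairment status at day 1". Protocol Appendix M, in its entry for Section 4.3, allows re-entry "following approval by the medical monitor and full screening assessments".

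Status is used in three outputs. It is a category in the baseline table (SAP 5.3), and it is a classifier, with weight group, in the weekly dose-level table (SAP 5.7). SAP 5.7 also reports the maintenance dose "nominal and as percent of the maximal planned dose for the patient", and SAP Tables 6 and 7 make the maximum depend on weight group and status.

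**The concern.** Carrying status forward would be right for a genotype, which does not change. Here status is a medication state, and a patient can start or stop an antidepressant between two participations. The rule therefore takes a changeable baseline value from the wrong day 1. It also pairs a new day 1 weight with an old status, although the two together determine the maximum dose.

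What is at stake is the accuracy of the dosing description. A patient titrated under one cap could be tabulated under the other. A dose above the cap of the row in which it appears would look like overdosing that did not happen. A patient now capped lower would look under-titrated. The SAP prevails where it differs from the protocol (SAP Introduction), so a programmer would follow the sentence as written.

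**Working it through.** The plan gives no figure on this point, so there is none to reproduce. The check compares the passages and then uses the documents' own dose maxima.

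**1. Is status fixed or changeable?** It is changeable. Neither document classes patients by genotype. Protocol Appendix K mentions CYP2D6 genotyping results once, in data-handling text, and the assessment schedules (Protocol Tables 4 and 5) list no genotype test.

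**2. Is there a new day 1?** Yes. Re-entrants are screened again in full and repeat the whole study. Protocol Table 4 has concomitant medication reviewed at screening and at day 1.

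**3. Can status change in the gap?** Yes. Protocol Section 5.5 prohibits adding a strong CYP inhibitor during the study and discourages removing one during treatment. Nothing extends either rule to the interval between participations, and Appendix M sets no limit on that interval. The inhibitors named are paroxetine, fluoxetine and bupropion. Protocol Table 11 requires antidepressants to have been stable for at least 6 weeks before screening or day 1, so a new user needs a gap long enough to meet that. Stopping carries no such wait.

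**4. Which outputs are affected?** The class label is wrong in SAP 5.3 and in the dose-level table of SAP 5.7 for any re-entrant whose status changed. This needs no further assumption.

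**5. What happens to percent of maximum?** This step assumes that the carried-over status sets the denominator and that the patient was titrated under the current status. Inputs are the maxima in Protocol Table 7. For a patient at the maximum for current status, the correct value is 100%.

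- Now impaired, old status not impaired: reported % = impaired maximum / non-impaired maximum × 100.
- No longer impaired, old status impaired: reported % = non-impaired maximum / impaired maximum × 100.

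| Weight group | Not impaired (mg) | Impaired (mg) | Now impaired | No longer impaired |
|---|---|---|---|---|
| 12 to <17 kg | 24 | 12 | 12/24 = 50.0% | 24/12 = 200.0% |
| 17 to <30 kg | 30 | 18 | 18/30 = 60.0% | 30/18 = 166.7% |
| 30 to <40 kg | 42 | 24 | 24/42 = 57.1% | 42/24 = 175.0% |
| ≥40 kg | 48 | 36 | 36/48 = 75.0% | 48/36 = 133.3% |

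**6. How many patients?** The documents do not say. Assuming 1 to 3 affected patients among about 45, the share is 1/45 = 2.2% to 3/45 = 6.7%. Zero is also possible.

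**The case against.** The strongest reply is that the distorted percentages need two things together: titration under the new status and scaling to the old one. SAP 5.7 does not say how the patient's maximal planned dose is found, and it could mean the cap under which the patient was dosed. On that reading, 48 mg in a ≥40 kg patient who is no longer impaired is 100%, not 133%. This stands. The percentages are conditional; the wrong class label is not.

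The reach is also small. A patient must stop because of an emergency, be approved to return, pass full screening, and have changed inhibitor use in between. This stands too.

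A reader might infer that results or compliance are affected. The documents do not support that. The study is descriptive (SAP 2.5), no efficacy subgroup is planned (SAP 6.3), and the only general safety split mentioned is an optional one by age group (SAP 8.1). Compliance uses each patient's expected dose from the supply system, not the maximum (SAP 5.8).

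A reader might also infer that re-entrants would be dosed under the wrong cap. The SAP sentence governs analysis, and nothing shows that it governs dosing.

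Finally, status re-derived from medication records alone could differ from the status used for dosing. That is a fair warning about the remedy, and the fix allows for it.

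**Conclusion.** The inconsistency is real and minor. As written, the rule misclassifies any re-entrant whose strong-inhibitor use changed between participations, in the baseline table and in the dose-level table by status. This rests only on the medication-based definition and the new day 1.

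The error in percent of maximum (50% to 75%, or 133% to 200%, in place of 100%) holds only if the carried-over status supplies the denominator and the patient was titrated under the current status. SAP 5.8 and SAP Tables 6 and 7 make that denominator plausible, but SAP 5.7 does not state it.

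It would go too far to say that every other baseline value is known to come from the re-entry. SAP 4.5.1 states a general rule, and CYP2D6 status is the only exception it names. The number affected is unknown and may be zero. No endpoint conclusion depends on this.

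**What to change.** Delete the carry-over sentence from SAP 4.5.1. State instead that, for re-entrants, CYP2D6 impairment status is the status at the re-entry day 1, meaning the one on which that participation's dose cap was based, checked against the concomitant medication records. Use it in SAP 5.3, in the dose-level table of SAP 5.7, and as the stated basis of the percent-of-maximum denominator. List the original status with the other data from the original participation.

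The cost is a short SAP edit, made before database lock. The medication data are already collected at screening and day 1. The one added task is to compare the status used for dosing with the medication records and to query any disagreement. The change concerns analysis classification only; it alters no dose and no clinical rule.

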4.5.2. Postbaseline Data

For each patient that re-entered the study, only data from the repeated participation will be included in the ITT analysis set. The original participation data will be listed separately and will not be included in any summary tables. In case of a SAE that occurred during the original participation and resolved prior to re-entering, the SAE will be documented in medical history database. Missing postbaseline data will be handled in the same method as other non-withdrawal patients.

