5.5. Medical History

All medical history will be coded using the Medical Dictionary for Regulatory Activities (MedDRA). The incidence of medical history abnormalities will be summarized using descriptive statistics by system organ class (SOC) and preferred term. Patients are counted only once in each preferred term and SOC category. Summaries will be presented for all patients.

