8. SAFETY ANALYSIS

8.1. General

Safety analyses will be performed on the ITT analysis set, unless otherwise noted. Summaries will be presented by overall patients. Selected safety data might also be presented by age group, as applicable.

For continuous variables, descriptive statistics will be provided for actual values and changes from baseline to each time point. For categorical variables, patient counts and percentages will be provided.

Summaries of potentially clinically significant abnormal values will include all post-baseline values (including scheduled, unscheduled, and early termination visits).

Safety assessments and time points are provided in [Table 3](#).

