8.2. Duration of Exposure to Study Drug

Duration of exposure to study drug (days) for individual patients is the number of days patient received drug (last day of study drug – first day of study drug + 1). Duration of treatment (days) will be summarized using descriptive statistics. Weeks on treatment using the categories ≤ 4 weeks, >4 to ≤ 7 weeks, >7 to ≤ 21 weeks, >21 to ≤ 27 weeks, >27 to ≤ 33 , >33 to ≤ 40 , >40 to ≤ 46 , >46 to ≤ 53 , and >53 weeks will also be summarized using descriptive statistics.

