8.3. Adverse Events

Adverse events will be collected and recorded from the time a patient signs the informed consent to the end of follow-up period. For this study, the follow-up period for recording of adverse events is defined as 2 weeks after the last dose of TEV-50717.

All adverse events will be coded using MedDRA. Each patient will be counted only once in each preferred term or SOC category for the analyses of safety. Unless otherwise specified, adverse events will be summarized by SOC and preferred term, with SOCs and preferred terms within SOCs presented in descending order of patient incidence. Summaries will be presented for all adverse events (overall and by severity), adverse events determined by the investigator to be related to test IMP (ie, reasonable possibility; see Table 9 of the study protocol - defined as related or with missing relationship), overall and by severity, serious adverse events, and adverse events causing withdrawal from the study. Most common adverse events, defined as occurring in $> 4\%$ of the patients in overall, and by preferred term. Summaries will be presented by all patients.

Summaries will include treatment-emergent adverse events which are defined as adverse events occurring at or after the first dose of the IMP. The listings will include all adverse events recorded.

Patient listings of all adverse events, serious adverse events, adverse events leading to study drug discontinuation, adverse events leading to dose interruption and adverse events leading to death will be presented.

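### SAP 4.5.2 keeps a re-entering patient's first-course adverse events, abnormal values and exposure out of every safety table; separately, the SAP leaves never-dosed patients in the safety denominator

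*SAP*

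**What the plan says.** **Re-entry.** Protocol Appendix M (its entry for Section 4.3) lets a patient terminated early because of an emergency come back, with medical monitor approval and full screening. It notes that such a patient "therefore, may receive treatment for more than 53 weeks". SAP 4.5 has the patient repeat the whole study, and SAP 4.5.1 generally takes baseline from the second participation.

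SAP 4.5.2 admits only the repeated participation to the ITT set. Of the first it says: "The original participation data will be listed separately and will not be included in any summary tables". It adds: "In case of a SAE that occurred during the original participation and resolved prior to re-entering, the SAE will be documented in medical history database". Serious events still ongoing at re-entry are not mentioned.

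**Rules elsewhere in the SAP.**
- 8.3, adverse events: "Summaries will include treatment-emergent adverse events which are defined as adverse events occurring at or after the first dose of the IMP". Each patient counts once per preferred term or system organ class. There is also a table of "Most common adverse events, defined as occurring in" more than 4% of patients.
- 8.1, abnormal values: "Summaries of potentially clinically significant abnormal values will include all post-baseline values (including scheduled, unscheduled, and early termination visits".
- 8.2, exposure: "Duration of exposure to study drug (days) for individual patients is the number of days patient received drug", computed as last day minus first day plus 1, with a top category above 53 weeks.
- 5.5, history: "The incidence of medical history abnormalities will be summarized using descriptive statistics by system organ class (SOC) and preferred term".

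**Never-dosed patients.** Protocol 9.6 uses the ITT set but removes patients who took no study drug from the safety summaries and only lists them. SAP 3.1 and 8.1 run safety on the ITT set, which includes them, without that exclusion. SAP 3.2 offers a dosed-only set, as exploratory. The SAP Introduction gives the SAP precedence over the protocol, and SAP Section 11 declares no changes from it.

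**The concern.** Long-term safety is the primary objective, there is no hypothesis test, and the incidence tables carry the conclusion. SAP 4.5.2 takes events that occurred on study drug, in enrolled patients, out of those tables. The record is kept in listings; what is lost is its place in the counts.

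The omission also runs in one direction. A patient who had an event in the first course and none in the second is tabulated as event-free. If the event was serious and resolved, the only table that can show it is the medical history table, where it looks like a condition that preceded treatment. The exposure table shows one course for a patient who had two.

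The never-dosed point works the same way on a smaller scale: a patient who could not have an on-drug event stays in the denominator and dilutes every percentage.

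**Working it through.** The plan has no powered figure to reproduce. SAP 2.5 gives about 45 patients and says the number has no statistical basis. The inputs are N = 45, the once-per-term rule and the 4% cut-off (SAP 8.3), the exposure formula (SAP 8.2), first dose on day 2 (SAP 4.4) and the scheduled visit days (SAP Table 3). The numbers of re-entrants and of never-dosed patients are not given, so one patient is assumed where a count is needed.

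**1. Direction.** For a re-entrant, let e1 and e2 be 1 if the term occurred in the first or second participation, otherwise 0. Counting both gives max(e1, e2); SAP 4.5.2 gives e2. Since e2 ≤ max(e1, e2) and the denominator is unchanged, incidence falls or stays the same. Enumerating every pattern for 0 to 4 re-entrants found no exception. This holds for whole-period patient-level incidence. By-visit percentages can move either way, and a count of mild events can rise if worst severity is tabulated and the severe first-course event is dropped.

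**2. Size per re-entrant.** If the term occurred only in the first course, the loss is 1/45 = 2.2 percentage points.

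| Patients with the term | Incidence | Clopper-Pearson 95% interval | Above 4%? |
|---|---|---|---|
| 0/45 | 0% | 0 to 7.9% | no |
| 1/45 | 2.2% | 0.06 to 11.8% | no |
| 2/45 | 4.4% | 0.5 to 15.1% | yes |

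A single serious event thus becomes none. Since 4% of 45 is 1.8 patients, a term needs two patients to enter the common-event table, so one exclusion can remove it. The same is true at the 42 enrolled when Amendment 04 was issued: 2/42 = 4.8%, 1/42 = 2.4%.

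**3. Exposure left out.** Assume a first exit at week 7, 27 or 40 (days 49, 189, 280) and a complete second course at nominal visit days. Days on drug = last day − 2 + 1.

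| First exit | First course | Second course (day 2 to 371) | Total | Weeks |
|---|---|---|---|---|
| day 49 | 48 | 370 | 418 | 59.7 |
| day 189 | 188 | 370 | 558 | 79.7 |
| day 280 | 279 | 370 | 649 | 92.7 |

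The second course alone is 370/7 = 52.9 weeks. A patient treated for about 60 to 93 weeks would be placed in the category ending at 53.

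**4. Never-dosed patients.** With one such patient, the understatement for x cases is x/44 − x/45 = x/1980:
- x = 1: 0.05 points
- x = 9: 0.45 points
- x = 30: 1.52 points

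**The case against.** **It may never apply.** No re-entrant is reported, the route is narrow, and Appendix M lapses at a site once normal activity resumes. That is fair: the effect is conditional and may be zero. Re-entry is still plausible. Enrolment rose from 8 to 42 between June 2020 and June 2022 with these provisions in force, and Appendix M extends to other crises.

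**Specific overrides general.** SAP 4.5.2 can be read as the particular rule for re-entrants, with 8.1 and 8.3 silent on re-entry; the more-than-53-weeks remark concerns conduct, and Protocol Section 9 leaves analysis detail to the SAP. This resolves which rule a programmer follows. It does not make the tables complete: Protocol 9.6 promises summaries of all adverse events, and the rule as followed omits some.

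**Other safeguards exist.** Listings, 24-hour reporting of serious events, the monitoring committee and the required account of emergency deviations in the study report do not depend on these tables. They protect patients and readers, but they do not correct the incidence figures.

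**Pooling has a cost.** Re-entrants would be observed longer than others, with two titrations and two baselines, so a single-course table alongside a pooled one is defensible. Summed exposure makes the difference visible.

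**Little will change in the discontinuation table.** An emergency exit is not normally an adverse-event withdrawal. That stands, although Appendix M (entry for Section 3.5) lets safety assessments enter the decision to terminate early when a clinic visit is impossible.

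**The never-dosed point is minor.** Agreed. SAP 5.2 also reports enrolled-but-untreated patients, so a reader could see the difference.

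**Conclusion.** The concern holds. Applied exactly as written, SAP 4.5.2 yields incomplete primary safety and exposure tables whenever a patient re-enters after a first-course event, and the error always flatters whole-period incidence. At N of about 45, each affected re-entrant costs 2.2 points per term, enough to turn one serious event into none or to move a term below the 4% cut-off. About 60 to 93 weeks of treatment would be shown as about 53, given the assumed exit times and a completed second course. If nobody re-entered, there is no effect.

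The re-entry rule is what makes this necessary to correct before database lock. The never-dosed conflict is real, but on its own it would be a wording reconciliation: 0.05 to 1.5 points for one assumed patient, and zero if every enrolled patient was dosed.

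**What to change.** **SAP 4.5.2.** For re-entrants:
- Include events from the first dose to 2 weeks after the last dose of each participation in the adverse event, serious adverse event and discontinuation tables, counting each patient once per term.
- Include post-baseline values from both participations in the potentially clinically significant and QTcF-prolongation tables, judging change criteria against the baseline of the participation in which the value was measured.
- Keep first-participation serious events as serious events, whether resolved or ongoing at re-entry.
- Retain the second participation alone for by-visit change tables and final disposition, and add a disposition row with the number of re-entrants and the reason for first exit.

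**SAP 8.2.** Sum the two dosing intervals, leaving out the off-drug gap.

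**SAP 3.1, 3.2 and 8.1.** Make patients with at least one dose the main set for all safety summaries and only list the never-dosed, as in Protocol 9.6.

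**SAP Section 11.** Record both points.

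The cost is SAP wording and a small programming change before lock; no new data are needed. The price is slightly less favourable incidence figures, and longer observation for re-entrants than for the rest.
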